**Table 1: PPoS based on responses among the first 20 patients pretreated with bevacizumab**

No. of responses* among the first 20 patients	PPoS
	PROC bevacizumab pretreated ( $p_0=12\%$ )
0	<1%
1	4%
2	20%
3	49%
4	77%
5	93%
6	99%
7	>99%

8	>99%
9	>99%
10+	>99%

\*  $P_0$  is the response rate of current standard of care of each cohort

If the PPoS is <10% (i.e., 1 or fewer responses among the first 20 patients), the interim data indicates that it is unlikely the ORR will be better than the response rate of current standard of care at the end of the cohort and the cohort could be stopped early due to insufficient activity. On the other hand, if the PPoS is >70%, the interim data suggests that if the same trend continues, there is a high probability to conclude a “success” at the end of the cohort. The PFS, OS, and DOR will also be evaluated at the time of the interim futility analysis using Kaplan-Meier methodology. Based on the activity and safety data, together with the PPoS, the cohort may continue or be stopped early by the sponsor. A cohort or Part may also be discontinued at any point at the discretion of the sponsor.

The operating characteristics of the design based on 500,000 simulation runs are summarized in Table 2. If the true ORR is less than 5%, there is reasonable chance to reach the futility criterion at interim. On the other hand, if the true ORR is 20% or higher, the probability to stop for futility is low (<12%).

**Table 2: Operating characteristics of predictive probability design**

True ORR	Pr(Futility*)	Final Analysis (N=60) PROC bevacizumab-pretreated		
		Pr(obs. ORR $\geq$ 15%)	Pr(obs. ORR $\geq$ 20%)	Pr(obs. ORR $\geq$ 25%)
5%	74%	<1%	<1%	<1%
10%	39%	13%	1%	<1%
15%	18%	52%	17%	3%
20%	7%	84%	54%	20%
25%	2%	96%	84%	55%
30%	<1%	>99%	97%	84%
35%	<1%	>99%	>99%	96%

\* 1 or fewer responders among the first 20 patients in the Part B bevacizumab pretreated cohort

Interim data from the study may be presented at scientific meetings such as the annual meetings of the American Society of Clinical Oncology and the European Society for Medical Oncology.

## 9 CHANGES FROM PLANNED ANALYSES

### 9.1 Changes from the Original Protocol

Not Applicable.

### 9.2 Changes from the Original SAP

Update SAP version 2 to align with SGNTV-002 Protocol Amendment 4.

## **Appendix A IMPUTATION OF PARTIALLY UNKNOWN ADVERSE EVENT DATES**

The algorithm below should be used to impute adverse event (AE) start dates for which only partial information is known. The algorithm should be applied to every AE record on a record by record basis. AE start dates should be imputed before imputation of AE condition end date in all cases. The AE condition end date should only be used in the imputation of the AE start date if it is a complete, known date.

### **AE day and month are missing**

- If the year is the same as the year of first dose of study treatment and the onset period and/or onset time indicate that the start of the AE was pre-dose:
  - AE start date will be imputed as the minimum of (AE condition end date\*, day prior to first dose of study treatment)
- If the year is the same as the year of first dose of study treatment and the onset period and/or onset time indicate that the start of the AE was post-dose:
  - AE start date will be imputed as the minimum of (AE condition end date\*, first dose date of study treatment)
- If the year is before the year of first dose of study treatment:
  - AE start date will be imputed as the minimum of (AE condition end date\*, December 31st see example 2 below)
- If the year is after the year of first dose of study treatment:
  - AE start date will be imputed as the minimum of (AE condition end date\*, January 31st see example 2 below)

### **AE month only is missing**

- Treat day as missing and replace both month and day according to the above procedure

### **AE day only is missing**

- If the month/year is the same as the month/year of first dose of study treatment and the onset period and/or onset time indicate that the start of the AE was pre-dose:
  - AE start date will be imputed as the minimum of (AE condition end date\*, day prior to first dose of study treatment)
- If the month/year is the same as the month/year of first dose of study treatment and the onset period and/or onset time indicate that the start of the AE was post-dose:
  - AE start date will be imputed as the minimum of (AE condition end date\*, first dose date of study treatment)
- If the month/year is before the month/year of first dose of study treatment:

- AE start date will be imputed as the minimum of (AE condition end date\*, last day of the month)
- If the month/year is after the month/year of first dose of study treatment:
  - AE start date will be imputed as the minimum of (AE condition end date\*, last day of the month)

\* Only use condition end date if known and complete end date is available.

The following algorithm should be used to impute AE condition end dates. The AE records for a condition/event should be sorted by the imputed start dates then record position (order of entry into the eCRF). After sorting, if any condition end date month/year is greater than any subsequent record end date month/year, then change the imputed start day only to end of month. Repeat as necessary.

After sorting the AE records, apply the following rules to partial or missing AE condition end dates:

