### 7.6.1 Adverse Events

AEs will be summarized by MedDRA preferred term in descending frequency of occurrence unless otherwise specified. For incidence reporting, if a patient reports more than one AE that was coded to the same system organ class or preferred term, the patient will be counted only once for that specific system organ class or preferred term.

Treatment-emergent AE (TEAE) is defined as a newly occurring or worsening AE after the first dose of study treatment and with onset date on or before 30 days after the last dose of study drug. See Appendix B for details regarding treatment-emergent classification.

Summaries of AEs will be provided by cohort and total for the following:

- TEAEs
- Grade 3 or higher TEAEs
- DLTs
- TEAEs by system organ class and preferred term
- TEAEs by system organ class, preferred term, and maximum severity. At each system organ class or preferred term, multiple occurrences of events within a patient are counted only once at the highest severity
- TEAEs related to tisotumab vedotin
- TEAEs leading to dose delay
- TEAEs leading to dose reduction
- TEAEs leading to dose elimination
- TEAEs leading to unplanned dose adjustment
- TEAEs leading to treatment discontinuation
- TEAEs leading to death
- Infusion related reactions

- Treatment-emergent SAEs
- Treatment-emergent SAEs by system organ class and preferred term
- Treatment-emergent SAEs related to tisotumab vedotin
- Treatment-emergent Adverse Events of Special Interest (AESI) by system organ class, preferred term and maximum severity
- Treatment-emergent AESI
- Serious AESI

All TEAEs, Treatment-emergent SAEs, TEAEs leading to treatment discontinuation, TEAEs leading to death, and DLTs will be listed.

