**Post imputation**

Start date	Condition end date	Severity	Outcome
31DEC2011	15APR2012	1	not recovered/resolved
15APR2012	31MAY2012	2	recovering/resolving
31MAY2012	30JUN2012	1	not recovered/resolved
30JUN2012	30JUN2012	3	recovering/resolving
30JUN2012	10JUL2012	2	recovering/resolving
10JUL2012	--	1	not recovered/resolved

*Example 2 (highlights choice of last day of the month as opposed to the 1st or the 15th)*

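### A missing AE start day in the month containing last dose + 30 days can remove a true treatment-emergent event from the TEAE tables

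*SAP*

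**What the plan says.** Four pieces of the SAP act together.

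- **Imputation rule.** In Appendix A, for a start date lacking only the day: "If the month/year is after the month/year of first dose of study treatment", the rule is "AE start date will be imputed as the minimum of (AE condition end date" and the last day of the month). A footnote limits the first term: "Only use condition end date if known and complete end date is available".
- **Use of the imputed date.** Section 6.5 says that imputed AE dates feed both event duration and treatment-emergent status.
- **TEAE window.** Section 7.6.1 defines a TEAE as new or worsening after first dose, "with onset date on or before 30 days after the last dose of study drug". Protocol 9.3.8.2 sets the same limit.
- **Cross-reference.** Section 7.6.1 sends the reader to Appendix B for the treatment-emergent classification. Appendix B deals only with start dates of subsequent anticancer therapy.

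Month end is a deliberate choice: the note to Example 2 says that it "highlights choice of last day of the month as opposed to the 1st or the 15th". The sort step in Appendix A suggests that the purpose is to keep successive records of one event in order.

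**The concern.** The date used to order records also decides whether an event counts as treatment-emergent. In the month that contains last dose + 30, month end lies beyond the window unless the window happens to close on a month end. An event that began before the cut-off is then dated after it. Nothing in the SAP caps the imputed start at last dose + 30, and nothing keeps an event whose partial date is compatible with the window.

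At stake are the TEAE summaries in SAP 7.6.1 (overall, Grade 3 or higher, related, and treatment-emergent AESI) and the planned AE listings, which are confined to TEAE categories and DLTs. Leaving out true post-dose events is the anti-conservative direction for a safety report.

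**Working it through.** **Reproducing the SAP's example.** In Appendix A Example 1 (first dose 01JAN2012) the rule gives UNUNK2011 → 31DEC2011, UNMAY2012 → 31MAY2012 and UNJUN2012 → 30JUN2012 (twice). All match the printed dates.

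**One case.** Last dose 10MAR2021, so the window closes on 09APR2021; the first dose was in an earlier month.

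- True onset 05APR2021, recorded as UNAPR2021, no complete end date: imputed 30APR2021, so not a TEAE.
- Same event, end date 08APR2021: imputed 08APR2021, kept.
- Same event, end date 20APR2021: imputed 20APR2021, lost.
- True onset 25MAR2021, recorded as UNMAR2021: imputed 31MAR2021, kept.

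**General count.** Assume no complete end date, onset evenly spread over days, and every 2021 last-dose date equally likely. If the window closes on day d of a month with L days, all d onset-days of that month up to the cut-off are lost when d < L, and none when d = L. Summing d from 1 to L − 1 gives L(L − 1)/2 per month:

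- seven 31-day months: 7 × 465 = 3,255
- four 30-day months: 4 × 435 = 1,740
- February: 378
- total: 5,373 lost onset-days, arising from 365 − 12 = 353 of 365 last-dose dates

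The denominator depends on which part of the window is considered. The whole window has 7w + 31 days for w weeks from first to last dose.

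| Part of window | Onset-days | Lost |
|---|---|---|
| Last 31 days | 365 × 31 = 11,315 | 47.5% |
| 30 days after last dose | 365 × 30 = 10,950 | 49.1% |
| Whole, w = 6 | 365 × 73 = 26,645 | 20.2% |
| Whole, w = 12 | 365 × 115 = 41,975 | 12.8% |
| Whole, w = 24 | 365 × 199 = 72,635 | 7.4% |
| Whole, w = 36 | 365 × 283 = 103,295 | 5.2% |

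**With a complete end date.** Among onsets in the 30 days after last dose, the loss is 6%, 18%, 33% and 49% for events lasting 3, 7, 14 and 28 days. The end-date cap therefore protects short events and does little for long ones. Unresolved events get no imputed end date and have no protection.

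**Direction.** Neither month end nor a complete end date can precede the true onset. This branch therefore never brings a late event into the window; at the upper bound it only removes true TEAEs.

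**The case against.** The strongest reply is that the exposure is narrow. Most of that reply stands.

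- **Not all partial dates go to month end.** "If the month/year is the same as the month/year of first dose of study treatment" and onset is post-dose, the first dose date is used (unless the sort step intervenes: "then change the imputed start day only to end of month"). With day and month both missing, a post-dose onset in the first-dose year also goes to the first dose date. "If the year is after the year of first dose of study treatment", January 31st is used. A complete end date caps all of these. Month-end dates in earlier on-treatment months remain TEAEs.
- **Records are not incidence.** SAP 7.6.1 counts a patient once per preferred term, so a lost record matters only if that patient has no other TEAE with that term.
- **Other outputs remain.** Protocol 9.3.8.2 tabulates all AEs and 9.3.8.3 lists SAEs. SAP 7.6.1 summarises serious AESI without a treatment-emergent restriction, SAP 7.6.3 covers all deaths, and SAP 6.1 provides for submission of all clinical data as data sets.
- **Onset dates are sought.** Under Protocol 7.7.8.4, SAEs and all ocular AEs are reported within 24 hours on a form that includes the onset date. The end-of-treatment contact at 30 to 37 days falls as the window closes. This makes partial dates less likely, not impossible.

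Three stronger readings are tempting and not supported. A reader might infer that nearly all partial-date TEAEs are lost. Within the closing month the share is indeed 94% (5,373 of 5,738 onset-days), but that is almost true by construction and says nothing about the rest of the window. A reader might infer that the events vanish from the report; the outputs above show otherwise. A reader might also infer that AESI time to onset should use the first of the month. Under even onset, month end is late by 14.7 days on average (5,373/365), and the first of the month is early by the same amount, so nothing is gained. Nor is the whole algorithm biased late, since the first-dose-date branches impute early.

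None of this supplies a rule for the closing month, which is the gap.

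**Conclusion.** The rule is wrong as written for one defined case: day missing, a month after the first-dose month that contains last dose + 30 without ending on it, and no complete end date inside the window. In that case a true TEAE is classed as not treatment-emergent, with no offsetting error at that bound.

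The percentages are shares of missing-day records without a complete end date, and they rest on evenly spread onset and last-dose dates. The documents do not say how many such records to expect. The absolute effect is therefore unknown and probably small. The primary endpoint is unaffected and the study has no formal hypothesis test. The point concerns the accuracy of safety tables and merits correction before database lock.

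**What to change.** In SAP Appendix A, keep month-end imputation for ordering records and add a separate rule for the TEAE flag. An AE recorded as starting after first dose, with a partial start date, is treatment-emergent unless its known month and year fall wholly after last dose + 30 days. Capping the imputed start at last dose + 30 whenever the partial month overlaps the window gives the same flag. Appendix A already uses last dose + 30 as a limit for some year-only end dates. In SAP 7.6.1, replace the reference to Appendix B with one to the new rule. Leave AESI time to onset as it is.

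The cost is a few sentences and a small programming change, plus some over-counting. With 12 weeks from first to last dose and AEs recorded to day 37, lost onset-days fall from 5,373 of 41,975 (12.8%) to 0. In exchange, 2,219 of 2,555 onset-days on days 31 to 37 after last dose (87%) would be counted as TEAEs when the day is missing. That is the conservative direction, and the SAP should say that it is accepted.

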#### **6.5 Handling of Dropouts and Missing Data**

Missing data will not be imputed unless otherwise specified. Missing AE start date and/or end date will be imputed while calculating duration of events and treatment-emergent status (see Appendix A for imputation details).

For time-to-event endpoints, e.g., DOR, PFS, and OS, patients who have no specific event will be censored as specified for each respective endpoint in Section 7.5.

Patients who do not have at least 2 post-baseline response assessments (initial response and confirmation scan) will be counted as non-responders for analysis of the primary endpoint.

Missing subsequent anticancer treatment start date will be imputed while deriving the time-to-event endpoints as applicable (see Appendix B for imputation details).

For prior therapies end dates, if month and year are present and only day is missing, day may be imputed. The end day will be imputed with the last day of the month or 21 days before the first dose of study drug, whichever is earlier. If the imputed end date is earlier than start dates, the end day will be imputed with the day after the start date. If month or year is missing, no imputation will be performed.

For prior therapies start dates, if month and year are present and only day is missing, day may be imputed. The imputed day will be the first day of the month. If month or year is missing, no imputation will be performed.

Unless otherwise specified, if the numeric value of a clinical laboratory test is not available because it is below the lower limit of quantification (LLOQ), “< LLOQ” should be used whenever applicable. In cases where a numeric value is required, e.g., calculating the mean and standard deviation, the LLOQ/2 will be used for the calculation.

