#### **7.6.1.1 Adverse Events of Special Interest**

Adverse events of ocular AEs, peripheral neuropathy, and bleeding are considered AESI. The search criteria for AESI will be maintained in a separate document and will be finalized prior to database lock. Shift tables comparing the highest post-baseline to baseline CTCAE grade will be presented when applicable.

Time to onset will be summarized for subjects who have the events that meet certain search criteria. Time to onset is defined as time (days) from the date of first dose to the start date of first event (start date of first event – date of first dose + 1).

Time to resolution will be summarized for events that meet certain search criteria and have the outcome of ‘recovered/resolved’ or ‘recovered/resolved with sequelae’. Time to resolution is defined as time (days) from the start date of the event to the end date of the same event (end date of the event – start date of the event + 1).

For events that are not resolved, improvement is defined as a decrease by at least one grade from the worst grade as of the latest assessment. For events that meet the definition of ‘improvement’, time to improvement will be calculated as time from the worst grade of the event to the date the event is improved.

Time to onset, resolution and improvement will be summarized by descriptive statistics (mean, standard deviation, median, minimum, and maximum). Time to onset will be summarized at the subject level. Time to resolution and improvement will be summarized at the event level.

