#### **For all records excluding the last chronological record for a condition/event**

- AE condition end date will be imputed as the start date of the subsequent record

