#### **For the last chronological record for a condition/event**

- If outcome is “recovered/resolved”, “recovered/resolved with sequelae”, or “fatal” apply the following:
  - If only year is provided for the end date and year is equal to the year of the last dose date:
    - AE condition end date will be imputed as the minimum of (last dose date+30, death date, data extraction date, December 31st of the end date year)
  - If only year is provided for the end date and year is not equal to the year of the last dose date:
    - AE condition end date will be imputed as the minimum of (death date, data extraction date, December 31st of the end date year)
  - If month and year are provided for the end date:
    - AE condition end date will be imputed as the minimum of (death date, data extraction date, last day of the end date month/year)
- If outcome is “recovering/resolving”, “not recovered/resolved”, “unknown”, or blank:
  - AE condition end date will not be imputed.

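### SAP Appendix A's re-ordering step for multi-record adverse events cannot correct records that end in the same month, or a later record with a year-only start, so some records are put in the wrong order and wrongly left open

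*SAP*

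**What the plan says.** SAP section 6.5 states the purpose: "Missing AE start date and/or end date will be imputed while calculating duration of events and treatment-emergent status". Appendix A then works in four steps.

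1. **Start date, record by record.** With only the day missing, the start is the earlier of the record's own complete end date and a default. The default is the last day of the month, or the first dose date if the month is that of first dose and onset was post-dose. A year-only start in the year of first dose, with post-dose onset, also defaults to the first dose date. Partial end dates are ignored.
2. **Sort.** Records of a condition are "sorted by the imputed start dates then record position (order of entry into the eCRF"), so entry order only breaks ties.
3. **Repair.** After sorting, "if any condition end date month/year is greater than any subsequent record end date month/year, then change the imputed start day only" to the end of the month, repeating as needed.
4. **End date.** For a partial or missing end on any record but the last, "AE condition end date will be imputed as the start date of the subsequent record". For the last record, if the outcome is recovering/resolving, not recovered, unknown or blank, "AE condition end date will not be imputed".

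SAP section 7.6.1.1 summarises time to resolution for AESIs whose recorded outcome is resolved. For those not resolved, "improvement is defined as a decrease by at least one grade from the worst grade as of the latest assessment".

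**The concern.** The repair exists to keep records in their true sequence, and Example 2 comes out right only because it fires there. But it tests for a strictly greater end month, so it is silent when two records end in the same month. When it does fire, it can only move a day within the month already imputed, so it cannot rescue a record placed in the wrong month.

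Once the order is wrong, the end-date rules carry the error on. The true last record is closed at the start of a misplaced one, and the misplaced record may be left open. Protocol section 7.7.8.1 requires changes in AE severity to be recorded, so conditions with several records are expected. Patients on the dose-dense schedule have eye examinations on Days 1, 8 and 15 of each cycle (Protocol sections 6.4.1, 6.4.4 and 6.4.5), so more than one ocular grade change in a month is plausible.

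**Working it through.** Inputs: the Appendix A rules and its two worked examples. The rules were applied literally. A blank end date was handled two ways, ignored or treated as later than any date, and the results below are the same under both. Duration is end − start + 1 (SAP section 6.4.1).

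**The SAP's own examples.** All six rows of Example 1 reproduce. In Example 2 (first dose 01APR2012), record 3 starts at min(04MAY, 01APR) = 01APR and sorts before record 2 (25APR). Its end month, May, is greater than April, so the repair moves it to the end of April and restores the order. The result is 30APR2012, where the SAP prints the non-existent 31APR2012.

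**Variant of Example 1 (same-month tie).** Change 10JUL2012 to 25JUN2012 in both cells that print it, the end of record 5 and the start of record 6.

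- Record 4 (Grade 3, UNJUN to UNJUN): no complete end, so it starts 30JUN.
- Record 5 (Grade 2, UNJUN to 25JUN): min(25JUN, 30JUN) = 25JUN.
- Record 6 (Grade 1, ongoing): starts 25JUN.

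The sorted order is 1, 2, 3, 5, 6, 4. June is not greater than June, so record 5 does not trigger the repair. If record 6's blank end counts as later, the test fires, but record 6's start is known, not imputed, and record 4 is already at month end.

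| Record | Grade | Start | End |
|---|---|---|---|
| 3 | 1 | 31MAY2012 | 25JUN2012 |
| 5 | 2 | 25JUN2012 | 25JUN2012 |
| 6 | 1 | 25JUN2012 | 30JUN2012 |
| 4 | 3 | 30JUN2012 | not imputed |

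The Grade 3 record is now last and open, and the ongoing Grade 1 record is closed. The same order and open record arise for every transition date from 01JUN to 29JUN, 29 of the 30 days. On 30JUN the record-position tie-break saves the order.

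**Variant of Example 2 (same-month tie).** Let the nausea resolve on 28APR2012 instead of 04MAY2012. Record 3 starts at min(28APR, 01APR) = 01APR and sorts before record 2 (Grade 2, 25APR to UNAPR). April is not greater than April, so nothing moves. Record 2 is last with outcome recovering/resolving, so it stays open. Record 3 runs 01APR to 28APR, 28 − 1 + 1 = 28 days. In true order it cannot start before 25APR, so it lasts at most 28 − 25 + 1 = 4 days.

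**Year-only start (constructed).** First dose is 01JAN2012. One record runs 15APR2012 to UNMAY2012 and the next, with post-dose onset, UNUNK2012 to 10JUL2012. The second is imputed to 01JAN. July is greater than May, so the repair moves it to 31JAN, still before 15APR, and repeating changes nothing. Its duration is 162 days (31JAN to 10JUL), against at most 87 (15APR to 10JUL) in true order.

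**The case against.** The strongest reply is that this is an edge case with narrow reach. Much of that stands.

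- **One changed cell is not enough.** If only the end of record 5 becomes 25JUN2012, the Grade 3 record is misplaced but closed at 10JUL2012. If only the start of record 6 changes, it is closed at 30JUN2012. The open Grade 3 record needs the transition date changed in both cells, which is how Example 1 prints it.
- **Resolved events do not become unresolved.** A reader might infer this from the Example 2 variant. SAP section 7.6.1.1 selects events for time to resolution by recorded outcome, and Appendix A changes no outcome. Record 3 stays resolved on 28APR2012; what changes is its start, and the Grade 2 record that stays open.
- **Treatment-emergent status does not flip.** In both variants the misplaced records fall on or after first dose either way. A Grade 3 start pushed beyond 30 days after last dose would come from the month-end start rule, which already gives 30JUN2012 in the unmodified Example 1.
- **The year-only case is not shown to leave a record open.** That depends on the outcome of the record that sorts last, which the case does not fix. It shows a wrong order and duration only.
- **Data collection may make the pattern rare.** Onset and resolution dates are recorded for every AE (Protocol section 7.7.8.2), edit checks raise queries (section 8.2), and ocular AEs go on an SAE form that includes the onset date (section 7.7.8.4).

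None of this answers the core point. The stated rule, followed exactly, gives a wrong sequence in small variants of the SAP's own examples, and Appendix A has no other check on order.

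**Conclusion.** The defect is real and its reach is limited. It affects record order, listings and record durations, including AESI time to resolution if an event is taken as a record; the SAP does not say whether it means the record or the whole condition. It affects the AESI improvement summary only if the last sorted record is taken as the latest assessment, which the SAP also leaves open. On that reading, an AESI with the pattern of the Example 1 variant would change from improved (Grade 3 to Grade 1) to not improved.

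AE incidence, maximum-grade tables, the DLT endpoint and the ORR are unaffected. The documents give no basis for estimating how many conditions will have the pattern. The result assumes a literal reading of Appendix A and that entry order in the examples is the true sequence, as their printed results imply. The correction is worth making before database lock, but the main safety conclusions do not depend on it.

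**What to change.** Replace the sort-and-repair paragraph in Appendix A with an order fixed before days are imputed:

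1. Keep records with complete start dates in date order. Place records with partial starts by their known year and month, and use eCRF record position where that does not settle the order, including year-only starts. Query any condition where entry order contradicts complete dates.
2. Bound each imputed start to be no earlier than the previous record's start and no later than the earliest complete date in this or any later record.
3. Say how a start below the lower bound is moved. Month end, capped at the upper bound, keeps Example 2 at 30APR2012; moving it to the previous record's start would give 25APR2012. A year-only start has no recorded month, so use the previous record's start.
4. Apply the existing end-date rules in that order.

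Applied this way, the rule reproduces Example 1 and the corrected Example 2, and restores the order in all three variants. In the Example 1 variant, Grade 3 is closed at 25JUN2012 and Grade 1 stays open. One residue is that in the year-only case the earlier record closes on 15APR2012 although its recorded end is in May. A lower bound at the first day of that month would avoid this.

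Correct 31APR2012 to 30APR2012 in both places in Example 2. State in section 7.6.1.1 what counts as the latest assessment, and whether an event is a record or a condition. The cost is a paragraph or two of SAP text and a small program change, with no new data.
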